### 7.6 ASSESSMENT OF HOMOGENEITY

To evaluate difference among sites in the study, summaries of baseline variables and endpoints by site will be tabulated for the PP analysis set. Comparisons will be made across sites for selected baseline variables. Continuous baseline data will be compared across sites for the PP analysis set using one-way ANOVA; categorical data will be compared across sites using the chi-square test.

To assess consistency in the treatment effect on the primary endpoint and on continuous secondary endpoints across sites, two-way ANOVAs with the main effects of treatment group and site and with the treatment group by site interaction effect will be carried out on the PP and mITT analysis sets. An endpoint with an interaction effect that is not significant at the 0.15 level of significance will be considered as supporting the poolability of data across sites for the treatment comparisons on that endpoint. Otherwise, treatment comparisons within sites will be inspected to determine the direction and magnitude of the interaction; if treatment effect is consistent in direction across sites centers but only differs in magnitude across sites, poolability of sites for the endpoint analysis is also supported. Any site with fewer than six subjects (combined treatment and control) will be combined into a single pooled site for purposes of this analysis.

The above assessment of consistency will be repeated across the following subgroups, with appropriate descriptive statistics being presented for each treatment group within each subgroup category:

- Patient disease state
- Patients determined to be fluid responsive vs non-fluid responsive
- AKI measures in patients determined to increase serum creatinine levels from baseline vs decrease serum creatinine levels from baseline (AKI measures vs. no AKI measures)
- Enrollment time frame (0-6 hours, 6-12 hours, 12-24 hours)
- Sex

Dichotomous secondary endpoint data will similarly be analyzed for poolability using logistic regression analysis.

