9.3.3 Additional Data Collection

Other data points and associated times will be collected in addition to the analysis of the continuous data from the Starling SV system. Types of data points for collection are:

- Medical history
- Medications
- Volume of treatment fluid administered
- Urine output (to be recorded every 12 hours)
- Respiratory status
- Serum Creatinine level (every 24 hours +/- 4 hours , for 72 hour monitoring period and at 30 day discharge)
- Lactate level (per chart review, if available)
- Significant clinical events not previously identified for study data collection, e.g. cardiac arrest, CPR, intubation, extubation, placement of catheters (intravenous, arterial, urinary, etc), etc.
- Changes in mechanical ventilator status parameters

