12.4 Secondary and Exploratory Endpoints

Secondary objectives that have been pre-specified to be included in the formal statistical analysis will be tested in sequential fashion using the Holms step-down procedure for type-I error rate correction if and only if the primary objective passes according to the criteria outlined above. At the conclusion of the trial, the key secondary endpoints will be ordered sequentially from most significant to least significant. The endpoints will then be tested in order at adjusted levels of significance (i.e. E1: 0.05/k, E2: 0.05/k-1; E3: 0.05/k-2, where k=number of specified endpoints). Once an endpoint fails, all following endpoints will not be tested. Following is a list of key secondary endpoints:

Following is a list of key secondary endpoints for formal testing:

- Length of ICU stay (days) until subject is medically ready for discharge
- Number of days free from ventilator use (30 day period)
- Requirement for mechanical ventilation
- Number of days free from vasopressor use
- Changes in serum creatinine levels from baseline
- Requirement for renal replacement therapy (RRT)

Additional secondary endpoint have also been identified for testing, but will not be included in the formal statistical testing procedures for key secondary endpoints:

- Incidence of Adverse Events (AE)

- Number of ICU readmissions
- Mortality rate
- Mean volume of treatment fluid
- Incidence of Major Adverse Cardiac Event (MACE)
- Discharge location
- Mean difference in fluid balance at ICU discharge

Additional sub-analyses have been planned for the primary and key secondary endpoints. Primary and secondary endpoints will also be evaluated by the following subgroup analysis:

- Patient disease state
- Patients determined to be fluid responsive vs non-fluid responsive
- AKI measures in patients determined to increase serum creatinine levels from baseline vs decrease serum creatinine levels from baseline
- Enrollment time frame

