## 5 SAMPLE SIZE

Subjects will be randomly assigned in a 2:1 ratio to treatment with Starling SV or to treatment with standard of care, stratified by time window of enrollment (0-6 hours, 6-12 hours, and 12-24 hours). The primary effectiveness endpoint for this study is fluid balance at ICU discharge.

Minimum enrollment ( $N_{\min}$ ) in the study will be set at 120 subjects (80 Starling SV and 40 control) to power at 80% for demonstration of superiority of means for the secondary endpoint of creatinine levels as a measurement of change from baseline at 72 hours. The secondary endpoint for change in creatinine levels at 120 evaluable subjects displays 80% power at a two-sided alpha level of 0.05 to demonstrate superiority of Starling SV under an assumption of an average treatment effect of -1.4 mg/dL with a standard deviation of 2.5 mg/dL.

Under an assumption of an average treatment effect of -2 L with a standard deviation of 3 L, the sample size of 120 evaluable subjects provides 92.7% power in a test of superiority of means for the primary effectiveness endpoint at a two-sided 0.05 level of significance.

The trial will incorporate a sample size re-estimation (SSR) at the time of the interim look (after 90 patients have been evaluated for the key secondary endpoint) based on promise for superiority in the key secondary endpoint. Sample size re-estimation, described in further detail in Section 3.1, will result in a maximum of 210 total evaluable subjects, or no more than 1.75 times the minimum of 120.

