### 7.5 MULTIPLE COMPARISONS AND MULTIPLICITY

It is recognized that with a multiplicity of tests comes inflation in the chance of a false finding. Therefore, formal statistical testing will only be done for the following secondary endpoints:

- Changes in serum creatinine level from baseline to 72 hours (key secondary endpoint)
- Requirement for renal replacement therapy (RRT)
- Requirement for ventilator use
- Length of ICU stay (days) until subject is medically ready for discharge
- Number of hours with ventilator use (30-day period)
- Number of hours with vasopressor use

These endpoints will be tested in a hierarchical (sequential) manner in the order given above (and testing will only proceed if a significant beneficial treatment effect is detected in the primary endpoint). Specifically, the first secondary endpoint (change in creatinine) will be compared between treatments at a two-sided 0.05 level of significance. If significant in the direction favoring Starling SV, then Starling SV will be considered beneficial on change in serum creatinine level, and the next endpoint (ICU stay) will be compared between treatments at a two-sided 0.05 level of significance; otherwise the statistical testing will stop and Starling SV will not be considered statistically significantly beneficial on any secondary endpoint. If the treatment comparison is able to proceed to this next secondary endpoint of ICU stay, it will be carried out at the two-sided 0.05 level of significance. If the treatment comparison is significant in the direction favoring Starling SV, then Starling SV will be considered beneficial on this endpoint and testing will proceed in a similar manner for the remaining endpoints; otherwise, treatment comparisons will stop and Starling SV will not be considered beneficial on this second secondary endpoint of ICU stay nor on all endpoints after it in the above sequence.

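### SAP 7.6 checks consistency of the treatment effect by creatinine rise versus fall, a factor known only after randomisation and, at 72 hours or ICU discharge, the sign of the key secondary endpoint

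*SAP*

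**What the plan says.** SAP 7.6 first sets out a site-consistency check. It fits two-way ANOVAs with treatment, site and their interaction to the primary endpoint and the continuous secondary endpoints, in the PP and mITT sets. "An endpoint with an interaction effect that is not significant at the 0.15 level of significance" counts as support for pooling. If the interaction is significant, the comparisons within sites are inspected, and pooling is still supported when they differ only in size and not in direction.

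The section then says: "The above assessment of consistency will be repeated across the following subgroups". This is to be done "with appropriate descriptive statistics being presented for each treatment group within each subgroup category". The third subgroup is "AKI measures in patients determined to increase serum creatinine levels from baseline vs decrease serum creatinine levels from baseline", which the bullet recasts in brackets as AKI measures against no AKI measures. Neither the time of the rise or fall nor the AKI classification is defined.

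Protocol 12.4 has the same entry, introduced by "Primary and secondary endpoints will also be evaluated by the following subgroup analysis". The protocol synopsis names only patients whose creatinine increases. Protocol 9.3.3 collects creatinine every 24 hours "for 72 hour monitoring period and at 30 day discharge".

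Change in serum creatinine from baseline to 72 hours is the first secondary endpoint in the SAP 7.5 hierarchy. SAP 9.2.1.1 takes it at 72 hours or ICU discharge, whichever comes first. SAP 7.6 does not exempt it from this subgroup.

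**The concern.** A rise or fall from baseline needs a later creatinine value, so it cannot be known at randomisation. If treatment lowers creatinine, as the plan assumes, it also moves patients from the rise stratum to the fall stratum. Within a stratum the arms are then no longer comparable by randomisation. When the endpoint is creatinine change itself, stratifying on its sign removes most of the between-arm difference.

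At stake is how the supportive results read. If the device works as assumed, the sponsor's own tables would show a small creatinine effect in both strata, which could be taken as little benefit whether or not creatinine rises. The consistency check could also pass or fail for reasons unrelated to true heterogeneity.

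**Working it through.** **Inputs from the documents.** SAP 5 assumes a "treatment effect of -1.4 mg/dL with a standard deviation of 2.5 mg/dL", with 80 Starling SV and 40 control patients, and a primary effect of -2 L with SD 3 L. SAP 7.6 uses an interaction threshold of 0.15.

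**Assumptions not in the documents.** Creatinine change is normal with equal SDs, the control mean change m lies between -1 and +1 mg/dL, the true effect is constant, and the rise or fall is taken at the endpoint's own time.

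**The plan's own figures.** Two-sample t-test power, noncentral t with 118 df:
- Creatinine: noncentrality 1.4 / (2.5 × √(1/80 + 1/40)) = 2.89, power 81.8% (SAP: 80%).
- Primary: 2 / (3 × √(1/80 + 1/40)) = 3.44, power 92.7% (SAP: 92.7%).

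**Mean change within strata.** With mean μ, SD σ and a = -μ/σ:
- risers: μ + σφ(a)/(1 - Φ(a))
- fallers: μ - σφ(a)/Φ(a)

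Example for m = 0:
- Control risers: 2.5 × 0.3989/0.5 = 1.995. Starling risers (μ = -1.4, a = 0.56): -1.4 + 2.5 × 0.3410/0.2877 = 1.563. Difference -0.43.
- Control fallers: -1.995. Starling fallers: -1.4 - 2.5 × 0.3410/0.7123 = -2.597. Difference -0.60.

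| m | Share rising, control vs Starling | Risers, control vs Starling | Difference | Fallers, control vs Starling | Difference |
|---|---|---|---|---|---|
| -1 | 34.5% vs 16.9% | 1.672 vs 1.333 | -0.34 | -2.405 vs -3.157 | -0.75 |
| 0 | 50.0% vs 28.8% | 1.995 vs 1.563 | -0.43 | -1.995 vs -2.597 | -0.60 |
| +1 | 65.5% vs 43.6% | 2.405 vs 1.856 | -0.55 | -1.672 vs -2.147 | -0.48 |

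As fractions of the true effect these run from 0.34/1.4 = 24% to 0.75/1.4 = 54%. The two strata also differ from each other although the true effect is constant: at m = -1 by -0.34 - (-0.75) = +0.41 mg/dL, at m = +1 by about -0.07.

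**The SAP's decision rule.** Simulated trials of 80:40 with the two-way model:
- Interaction p < 0.15 alone: 12.9%, 13.1% and 13.4% at m = -1, 0 and +1, so not raised. A median split on an independent baseline factor gives 14.4% to 15.4%.
- Interaction p < 0.15 and opposite directions, which is what SAP 7.6 treats as inconsistent: 9.7%, 7.9% and 8.5%, against about 3% for the baseline split.

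**Sensitivity to shape.** With skewness of -2 to +2 (assumed) and a constant effect, the rate of interaction p < 0.15 runs from 2.8% to 54.5% for rise/fall, and from 14.5% to 15.6% for the baseline split.

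**2:1 allocation (secondary point b).** Same power formula, total N held fixed:
- Between arms in a subgroup of 60, 40:20 vs 30:30: 66.8% vs 71.9% (2 L, SD 3) and 52.0% vs 56.9% (1.4 mg/dL, SD 2.5).
- Within the Starling arm at N = 120, even split, standardised difference 0.667: 40 vs 40 gives 83.8%; the 30 vs 30 available under 1:1 gives 71.9%.

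**The case against.** The best case for the plan is that this is a supportive check. SAP 7.5 confines formal testing to a listed sequence, and SAP 9.2.1.1 estimates the creatinine effect by ANCOVA on baseline creatinine without this factor. That stands, and it limits the weight of the point.

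The wording is also ambiguous. The bracketed phrase may denote an AKI classification that is not defined, or the bullet may mean only that AKI outcomes are described in these patients. The time point is open too: at a time other than 72 hours or ICU discharge, the factor is not the sign of the endpoint and the distortion is smaller. So the sign-of-endpoint reading is likely rather than certain. On any of these readings the factor remains post-randomisation, and SAP 7.6 as written still puts it through the interaction assessment.

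Three stronger inferences are tempting, and the documents do not support them.
- A reader might average the two strata, get -0.55 to -0.51 mg/dL, and conclude that the trial would report about -0.5 instead of -1.4. SAP 7.6 neither reports nor acts on the two-way model's treatment term, and its value depends on coding.
- A reader might expect too many significant interactions. Under normality the p < 0.15 rate is not raised; it rises or falls only under assumed skewness.
- A reader might call the 2:1 rationale (protocol 8.6, SAP 2) simply wrong. It refers to sub-analysis by patient population without naming the comparison, and 2:1 does raise power for comparisons within the Starling arm.

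**Conclusion.** The point holds as a fault in a supportive analysis. The rise/fall factor should not be used to judge consistency of the treatment effect, because it arises after randomisation and treatment can change it.

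If the factor is taken at 72 hours or ICU discharge, and under the stated normality and control-mean assumptions, the tables understate the creatinine effect by roughly half to three quarters in each stratum. They can also show a spurious difference between strata of up to about 0.4 mg/dL. The SAP's rule would then declare a constant effect inconsistent about three times as often as it would with a baseline split. These sizes illustrate what could happen; the control mean and the distribution are not in the documents. The objection to a post-randomisation factor does not depend on them.

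Two secondary points also need attention.
- (a) Fluid-responsive status is not defined by which assessment or in which arms. Protocol 7.2 assigns dynamic assessment to the treatment group and prohibits its use to determine fluid responsiveness in controls, while protocol 9.3.2 lists a baseline assessment with no arm restriction. Figure 1 and the Appendix A algorithm are not shown and may settle the order.
- (b) The 2:1 rationale needs a stated comparison.

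**What to change.** In SAP 7.6, take creatinine rise/fall (AKI) out of the interaction assessment. State its time point and report it only as a descriptive table with the number of patients per arm, labelled post-randomisation and non-causal, with no treatment comparison or interaction test. If a renal subgroup is wanted for consistency, use baseline serum creatinine, below versus at or above the pooled median of the analysis set. Record this in the SAP as a change from protocol 12.4, as SAP 6.5 already does for the safety population.

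Secondary changes:
- (a) Reconcile protocol 7.2 with 9.3.2. Test a fluid-responsiveness interaction only if status is assessed in both arms before any arm-specific treatment; otherwise describe it in the Starling arm.
- (b) State which comparison the 2:1 rationale refers to. The allocation need not change.

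The cost is SAP wording before database lock. Protocol 9.1 already collects baseline creatinine, so no new data are needed. If the protocol text is edited as well, protocol 15.2 requires IRB approval before use. The downside is that one exploratory between-arm table is lost, the baseline split answers a different question from AKI development, and the fluid-responsiveness table may be limited to one arm.

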## 8 DEMOGRAPHICS AND OTHER BASELINE CHARACTERISTICS

### 8.1 DEMOGRAPHICS

Demographics will be summarized by treatment group for the PP and mITT analysis sets. There will be no formal statistical comparisons between treatment groups on demographic variables. The continuous variables of age, height (cm), weight (kg), BMI, qSOFA, SOFA, FiO2, and Glasgow Coma Score will be summarized by treatment group using sample size, mean, standard deviation, minimum and maximum. For the categorical variables of sex (male, female), race (white, black or African American, American Indian/Alaska Native, Asian, Native Hawaiian or Other Pacific Islander, other, unknown), ethnicity (Hispanic or Latino, Not Hispanic or Latino, Unknown), known or presumed infection, SIRS criteria exhibited (Temperature >38 C, Temperature <36 C, Heart Rate > 90/min, Respiratory rate >20/min or PaCO2 <32mm, White Blood Cell Count >12000/mm^3, White Blood Cell Count <4000/mm^3, White Blood Cell Count

[REDACTED]

>10% Immature Cells), smoking history (never, current, former), sepsis diagnosis (bacterial, fungal, viral, parasitic, other), Receiving Respiratory Support, and Cardiovascular Score (MAP  $\geq$  70 mmHg, MAP < 70 mmHg, Dopamine <5 or dobutamine (any dose), Dopamine 5.1-15 or epinephrine  $\leq$ 0.1 or norepinephrine  $\leq$ 0.1, Dopamine >15 or epinephrine >0.1 or norepinephrine >0.1), the number and percentage of patients in each category will be presented for each treatment group.

## 8.2 PRIOR AND CONCURRENT MEDICATIONS

A listing will be provided detailing subjects' medications, but no table is planned at this time.

## 8.3 BASELINE MEDICAL HISTORY

The medical history of all PP and mITT subjects will be summarized in a table by treatment group. For each condition, the number and percent of subjects who currently have the condition, who have a resolved history of the condition, and who have no prior history will be presented. The list of conditions is captured in the FRESH Medical History CRF.

## 8.4 BASELINE LABS AND VITAL SIGNS

A table presenting descriptive statistics (sample size, mean, standard deviation, median, min and max) of laboratory variables and vital signs by treatment group at baseline will be provided for the PP and mITT analysis sets. The laboratory variables are hemoglobin, serum creatinine, lactate levels, platelets, and bilirubin, and the arterial gases pH, PaCO2, PaO2, HCO3, O2CT, and O2SAT. The vital signs are body temperature (C), heart rate (bpm), respiration rate (breaths/min), pulse oximetry (%), systolic blood pressure (mmHg), and diastolic blood pressure (mmHg).

# 9 EFFICACY ANALYSES

All efficacy analyses will be performed on the PP analysis population (primary) and mITT analysis population (supportive).

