7.2 Study Design

This study is a prospective, multi-center, randomized trial comparing the mean difference in fluid balance and associated patient outcomes between a treatment guided by a dynamic assessment of fluid responsiveness and a standard of care control group not using dynamic fluid assessment. Between seven and fifteen sites will be used to enroll 210 subjects with the diagnosis of sepsis and refractory hypotension and in whom the Starling SV system can be attached. Subjects will be randomized in a 2:1 treatment to control group ratio. In the treatment group, a dynamic assessment of fluid responsiveness will be performed at every clinical decision point to treat hypoperfusion or impending hypoperfusion for the first 72 hours of study enrollment. Examples of a clinical decision point include a MAP of < 65, SBP < 90 or blood pressure that is rapidly trending lower, low urine output, or any other clinical indication to administer/alter fluid bolus or pressors. Additionally, an assessment of fluid responsiveness will be performed every 12 hours if no clinical assessments have taken place during this time period.

Fluid responsiveness will be assessed using a passive leg raise (PLR) to guide corresponding treatment (**Appendix A**). Continuous data will be collected from the Starling SV system during the entire treatment period. In the control group, no required therapeutic protocol will be used for patient treatment, and is determined per the discretion of the physician and hospital standards. The use of dynamic fluid assessment (i.e. SVV, PPV, or SV change) to determine fluid responsiveness within the control group is prohibited.

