### 6.3 MODIFIED INTENT TO TREAT POPULATION (MITT)

Subjects will be included in the Modified Intent-to-Treat (mITT) group if they sign the ICF, meet study eligibility criteria, are randomized, and in the treatment group receive monitoring for the first 72 hours of study enrollment or until ICU discharge, whichever occurs first. The mITT population will be conducted as a supportive analysis population for the primary and secondary endpoints.

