### 6.4 PER-PROTOCOL (PP)

Subjects will be included in the Per-protocol group if they sign the ICF, are randomized and have the assigned procedure completed, meet critical study eligibility criteria and have no major protocol deviations (to be pre-defined as an attachment to the interim and final analyses), and, in the treatment group, receive monitoring for the first 72 hours of study enrollment. The PP population represents the primary analysis population for the primary and secondary endpoints.

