### 6.5 SAFETY

Subject will be included in the safety group if they are in the ITT analysis population and study treatment was at least attempted. This is the primary analysis population for safety, including adverse events (this is a change from the protocol, where it states that adverse events will be reported on all enrolled patients; it has been since felt that this could underreport the true adverse event rates in patients to whom randomized treatment was attempted). Patients are analyzed under the treatment received.

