#### 9.2.2.3 Mortality Rate

The mortality rate will be summarized by treatment arm in a table. The summary will include the number and percent of subjects who died by arm; Kaplan-Meier mortality curves will be presented for each treatment group. Though no formal hypothesis tests are planned, 95% confidence intervals for the difference in rates between the two arms will be completed and included using the normal approximation to the binomial distribution or Wilson method (if an observed rate is less than 10% in any treatment group).

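### Mortality and MACE are compared in PP and mITT, whose monitoring condition applies to the Starling arm only, so early Starling deaths can leave the denominator while early control deaths stay in

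*SAP*

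**What the plan says.** Section 9 of the SAP opens with its population rule: "All efficacy analyses will be performed on the PP analysis population (primary) and mITT analysis population (supportive"). Mortality (9.2.2.3) and MACE (9.2.2.5) are listed under 9.2, the secondary efficacy variables, and neither names a set of its own. For mortality, "The summary will include the number and percent of subjects who died by arm", with Kaplan-Meier curves and a 95% confidence interval for the difference in rates. MACE is treated in the same way at 72 hours, one week and 30 days.

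Membership of the two sets depends on arm:

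- PP (SAP 6.4) asks that subjects, "in the treatment group, receive monitoring for the first 72 hours of study enrollment". It makes no exception for ICU discharge or death.
- mITT (SAP 6.3) asks that subjects "in the treatment group receive monitoring for the first 72 hours of study enrollment or until ICU discharge, whichever occurs first". It makes an exception for discharge but does not mention death.
- Neither set puts a monitoring condition on controls. Protocol 7.2 explains why none could apply: "In the control group, no required therapeutic protocol will be used for patient treatment".

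The ITT set (SAP 6.2) has no monitoring condition, but no section 9 endpoint is assigned to it. Of the Safety set, SAP 6.5 says: "This is the primary analysis population for safety, including adverse events". Section 10 runs the adverse event tables on mITT and Safety, and 10.3 adds a data listing of deaths.

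**The concern.** Death is the event being counted, and surviving the first 72 h in the ICU is, in one arm, close to a condition for being counted at all. Take two patients who die in the ICU at 30 h. The control is in both sets and scores as a death. The Starling patient has not had 72 h of monitoring and so is not in PP. If death is not ICU discharge, that patient is not in mITT either.

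This is a post-randomisation selection, in one arm, on a variable tied to survival, and the supportive set may share the fault of the primary one. A strategy meant to change fluid administration in sepsis with refractory hypotension will be judged partly on its mortality table, so the denominator of that table matters even without a formal test.

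**Working it through.** **The plan's own figures.** The documents give no mortality rate, no timing of deaths and no MACE rate, so there is no planned figure to reproduce for these endpoints. The design sizes used below come from SAP section 5: 80 Starling and 40 control, with a maximum of 210, which is 140 and 70 at 2:1. As a check on that base, a two-sample t-test with 80 and 40 subjects, a difference of 2 L, SD 3 L and two-sided 0.05 has 92.7% power, which matches the SAP.

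**Does ICU death count as ICU discharge?** The SAP does not define this. Its rule for ICU length of stay (9.2.1.4) handles death in the ICU apart from discharge, which supports the literal reading, though that rule concerns an endpoint and not membership of a set. If death did count as discharge, mITT would keep these patients. PP would still lose them, since 6.4 has no discharge clause.

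**mITT, literal reading.** Assume the same true mortality m in both arms, and let a share f of Starling deaths occur in the ICU before 72 h. With e = m × f, apparent Starling mortality is (m − e)/(1 − e), and control mortality stays at m.

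For m = 20% and f = 1/3: e = 0.0667, and (0.2000 − 0.0667)/(1 − 0.0667) = 0.1333/0.9333 = 14.3%. The difference is 14.3 − 20.0 = −5.7 points.

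| True mortality, both arms (assumed) | Early share (assumed) | Apparent Starling | Difference (points) | Risk ratio |
|---|---|---|---|---|
| 15% | 25% | 11.7% | −3.3 | 0.78 |
| 15% | 50% | 8.1% | −6.9 | 0.54 |
| 20% | 1/3 | 14.3% | −5.7 | 0.71 |
| 30% | 25% | 24.3% | −5.7 | 0.81 |
| 30% | 50% | 17.6% | −12.4 | 0.59 |

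Against sampling error, for the 20% and 1/3 case:

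- At 80:40, 80 × 0.9333 = 74.7 Starling subjects remain. SE = √(0.143 × 0.857/74.7 + 0.2 × 0.8/40) = 0.075, so the bias is 0.057/0.075 = 0.76 SE.
- At 140:70, 130.7 Starling subjects remain, SE = 0.057, and the bias is 1.0 SE.

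In reverse, a true Starling mortality of m/(1 − f + m × f) would look equal to m. For m = 20%, this is 0.2/0.84 = 23.8% at f = 20% and 0.2/0.60 = 33.3% at f = 50%.

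**PP.** Let a share g of Starling survivors also leave the set because they are discharged, and monitoring stops, before 72 h. Apparent Starling mortality becomes m(1 − f)/[m(1 − f) + (1 − m)(1 − g)]. With m = 20% and f = 1/3 (g assumed):

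- g = 0: 0.1333/(0.1333 + 0.8000) = 14.3%
- g = 1/3: 0.1333/(0.1333 + 0.5333) = 20.0%
- g = 1/2: 0.1333/(0.1333 + 0.4000) = 25.0%

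The bias is zero when g = f and reverses when g > f.

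**MACE.** The documents do not list its components, so no figure can be given. The events at risk of loss are those in Starling patients who die early.

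**The case against.** **Direction.** A reader might infer that both comparisons favour Starling by construction. The documents do not support that for PP, the primary set. The plan expects ICU discharges before 72 h, and PP as worded can drop those patients, mostly survivors, in the Starling arm. The net direction there is unknown, and the range of −3.3 to −12.4 points does not apply to PP.

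**mITT as a check.** A reader might also infer that mITT cannot act as a check on PP. That holds only if ICU death is not ICU discharge. The reading is supported by 9.2.1.4 but is not defined.

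**Placement.** Sitting in section 9 does not fully settle the population. TEAE incidence (9.2.2.1) sits there too, yet 6.5 and 10 send adverse events to the Safety set. MACE is an adverse event by name, so Safety is a plausible reading for it. That argues for stating the set, since 9.2.2.5 does not. It is weaker for mortality, because 10.3 treats its listing as additional to the secondary endpoint analysis.

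**Visibility.** It would be wrong to say that early Starling deaths vanish. Death meets the SAE definition (Protocol 10.1.2), and serious TEAEs are tabulated by arm in the Safety set; deaths are also listed. But Protocol 10.1 limits SAE collection to five organ areas and to the treatment period plus 48 hours, so those tables are not an assured count of deaths. A listing is not a comparison.

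**Weight.** Both endpoints are outside formal testing. No error rate and no primary conclusion depends on them. That stands.

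**Conclusion.** The point holds in limited form. On the current text, the mortality and MACE comparisons rest on two sets selected after randomisation, in the Starling arm only, on a variable tied to survival. Neither is a sound denominator for deaths.

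The size depends on the set. In mITT, if ICU death is not discharge, the bias lowers apparent Starling mortality: by 5.7 points at 20% true mortality with one third of deaths early, and by 3.3 to 12.4 points over the assumed ranges. Mortality and timing are assumptions throughout. In PP the selection is certain on the wording but its net direction is not. For MACE there is no figure.

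The consequence is for the safety picture and its confidence intervals. It does not extend to type I error or to the test of the primary endpoint.

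**What to change.** - In SAP 9.2.2.3 and 9.2.2.5, state that mortality and MACE are analysed in all randomised subjects by assigned arm, regardless of monitoring duration, with PP and mITT as supplementary only.
- In 6.3 and 6.4, state that a subject monitored until death before 72 h meets the monitoring condition.
- In 6.4, also state how ICU discharge before 72 h is handled. If only the death clause were added, PP would keep early deaths and still drop early-discharged survivors. With m = 20%, f = 0 and g = 1/3 (assumed), apparent Starling mortality would be 0.2/(0.2 + 0.5333) = 27.3% against 20%.
- In 9.2.2.1, name the Safety set for TEAEs, to agree with 6.5 and 10.

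The cost is SAP wording and one population flag on tables already planned. No new data are needed for mortality: Protocol Table 2 already requires deaths to be reported to the sponsor within 24 hours of knowledge.
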